# 2.1.1. Safety Population

The safety population will include all participants who receive at least 1 day of study drug. The safety population will be used for all tabulations of safety variables, unless otherwise specified in the SAP text or the table shell.

# 2.1.2. Full Analysis Set

The full analysis set (FAS) will consist of all evaluable participants, defined as all randomized participants who receive at least 1 day of study drug and have a baseline assessment on the ABC-SW and at least 1 primary efficacy assessment on the ABC-SW after administration of study drug. The FAS will be used for all tabulation of demographics and baseline characteristics, and the primary efficacy population and used in efficacy analyses.

#### 2.1.3. Per-Protocol Population

The per-protocol (PP) population is defined as a subset of FAS who complete the full 24 weeks of double blind treatment with study drug (including those who stayed on the study drug for at least 22 weeks with 80% treatment compliance) and all assessments of the ABC-SW at baseline, Weeks 4, 8, 12, 16, 20 and 24. The per-protocol population will be used only for supportive analyses of the primary efficacy endpoint.

### 2.2 General Summarization of Study Data

Unless otherwise specified, continuous variables will be summarized with descriptive statistics including n, mean, standard deviation (SD), median, first quartile (Q1) and third quartile (Q3) and minimum and maximum values. Categorical variables will be reported as number and percentage of participants in each category. Least squares (LS) means, standard errors, estimates of contrasts with 95% confidence intervals (CI), and p-values will be reported as appropriate.

All other statistical tests and confidence intervals will be 2-sided, unadjusted for multiplicity, and tested at  $\alpha$  = 0.05, except those explicitly stated to be otherwise.

All analyses and summaries will be produced using SAS® version 9.3 (or higher).

#### 2.3 Sequence of Planned Analyses

All analyses described in this SAP will be performed after data collection has concluded, the database locked, and the treatment blind has been broken. There will be no interim analyses of study data except for the summaries provided to the Data Safety Monitoring Board (DSMB).

An independent DSMB will meet twice yearly to review safety information for the study. The study's DSMB statistician will prepare summaries of data as described in the Safety Analyses section, separating them into treatment group A and treatment group B and will distribute them only to the members of the DSMB. No study team member other than the DSMB statistician will see the summaries provided to the DSMB.

Analyses for the primary manuscript as described in this SAP will focus on analyzing data during the 24-week double-blinded treatment period. Analyses on open-label treatment period (24-48 weeks) and the off-treatment follow-up period (>48 weeks) will be specified in separate analysis plans.

When performing analyses for the primary efficacy variable (ABC-SW), additional models with baseline serum oxytocin, age, and functionality as covariate will be examined and tested prior to analyzing data on the secondary efficacy variables.

## 2.4 Summary of Data Sources

Data collected at each center by investigators are entered into the ReDCAP database, and parents/guardians' responses on various measurements are entered into the Qualtrics database. The RMET data are entered into the Qualtrex participant database. Both RedCAP data and Qualtrics data are used for analysis.

#### 3. PARTICIPANT DISPOSITION ANALYSES

#### 3.1 General Summaries

Disposition will be summarized for all enrolled participants. Summaries will include counts of:

- Participants who were enrolled
- Participants who were enrolled but not randomized
- Participants who were randomized
- Participants who were randomized but did not take study drug
- Participants who were in the safety population
- Participants who were in the FAS
- Participants who were in the PP population
- Participants who completed the double blind portion of the study
- Participants who terminated the study early
- Participants with the each potential primary reason for early termination (i.e. adverse effect, inconvenience, administrative, lack of efficacy, noncompliance, lost to contact)

All summaries will be presented by treatment group and over all participants. A listing of disposition will be provided for all participants who did not complete the double blind portion of the study.

#### 3.2 Protocol Deviations

Protocol deviations will be recorded by each site as they occur and/or captured during monitoring visits. All protocol deviation data will be available upon request.

#### 3.3 Demographics and Baseline Characteristics

Demographics and baseline characteristics will be summarized by treatment group and over all participants for the FAS population. Demographic characteristics will include sex, age, race, and ethnicity. Clinical characteristics will include Autism Diagnostic Observation Scale (ADOS) severity scores. Baseline efficacy variables (see Efficacy Analyses section for list), vital signs, and female reproductive status will also be summarized.

[figure not shown]
Age (months) will be calculated as the number of months between date of birth and date of baseline visit. .

#### 3.4 Dose and Compliance

All dosing, exposure, and compliance information will be summarized by treatment group and over all participants for the FAS population.

Summaries of dose will include the percent of participants not able to tolerate the target dose, defined as those who were not at 48 IU TDD or higher at week 24, mean 24 week dose, and mean maximal dose.

Medication compliance will be evaluated each time the participant returns study medication at week 4, 8, 16, 20 and 24 using the formula below. The average of non-missing percent compliance per subject will be used to report mean treatment compliance for each treatment group.

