#### 1.2.2 SECONDARY OBJECTIVES

- To determine the efficacy of OT as measured by changes in ABC-SW scores as a function of baseline plasma oxytocin levels, age and functional level and the interaction of each with treatment, and with treatment and week.
- To determine the safety and tolerability of OT in participants with ASD as measured by incidence of treatment emergent adverse events (TEAEs) and abnormal laboratory values, tolerability of OT dose, and time to early termination.
- To determine the efficacy of OT as measured by changes in the sociability factor (SF), a combined measure formed from 13 items of the ABC-SW and the Pervasive Development Disorders Behavior Inventory –Screening Version (PDDBI-SV).
- To determine the efficacy of OT as measured by changes in ABC-SW scores in low-functioning and highfunctioning strata separately.
- To determine the efficacy of OT as measured by changes in Social Responsiveness Scale Version 2 (SRS-2) Social Motivation scores and Stanford Binet-5 Abbreviated IQ standard scores.

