#### 5. SAFETY ANALYSES

Safety and tolerability will be evaluated based on the incidence of TEAEs, incidence of elicited reports of suicidal ideation or statements, self-injurious behaviors, and suicidality, incidence of AEs leading to termination and changes in vital signs, modified BMI z-score, ECG findings and laboratory measurements, and incidence of pre-specified abnormal laboratory test results. All safety data will be presented using the safety population.

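### SAP v2.0 section 3.4 reports dose tolerability in the full analysis set, which leaves out treated children who stop before their first post-dose ABC-SW and return no form

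*Combined protocol and SAP*

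**What the plan says.** All references are to SAP v2.0 unless stated.

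- **Objective (1.2.2).** The safety and tolerability objective is to be measured by adverse events, abnormal laboratory values, and "tolerability of OT dose, and time to early termination".
- **Dose summaries (3.4).** "All dosing, exposure, and compliance information will be summarized by treatment group and over all participants for the FAS population". One of these results is "the percent of participants not able to tolerate the target dose, defined as those who were not at 48 IU TDD or higher at week"; the time point meant is the end of the 24-week blinded phase.
- **FAS (2.1.2).** Members must be randomised, receive at least one day of drug, and "have a baseline assessment on the ABC-SW and at least 1 primary efficacy assessment on the ABC-SW after administration of study drug".
- **Safety population (2.1.1).** "The safety population will include all participants who receive at least 1 day of study drug". It is the default for safety tabulations, unless the SAP text or a table shell specifies otherwise.
- **Safety analyses (5).** "All safety data will be presented using the safety population". No exception is attached.
- **Early termination.** Section 3.1 gives counts and primary reasons. Section 5 gives the incidence of adverse events leading to termination. Section 5.6 gives the DSMB a listing with duration of treatment. None of these is an analysis of time to termination.

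**The concern.** Tolerability of dose belongs to the safety objective, but section 3.4 reports it in a set whose membership depends on an efficacy form being returned after dosing. The children screened out this way include early stoppers, who bear most directly on whether the dose could be tolerated. At stake is a tolerability percentage that is slightly too low within an arm, and dose and exposure tables whose denominators differ from those of the adverse-event tables.

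A second, smaller inconsistency is that time to early termination is a named measure with no planned analysis.

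**Working it through.** **1. Who is left out, and how the SAP's definition would class them**

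- The first scheduled post-dose ABC is at week 4 (SAP Table 1; protocol v6.0 section 6.2).
- In the blinded phase the suggested titration does not allow 48 IU total daily dose before week 8 (protocol v6.0 section 5.2).
- Non-tolerance in SAP 3.4 means not being at 48 IU per day or higher at week 24.

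A treated child who stops before week 4 and returns no ABC is thus in the safety population, outside the FAS, and non-tolerant by definition. That child is in neither the numerator nor the denominator of the 3.4 percentage.

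**2. How many: the plan's own figures**

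SAP section 6 requires 71 per group in each of two strata: 71 × 4 = 284. Allowing for attrition before the first post-randomisation visit:

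- 5%: 284 / 0.95 = 298.9, so 299 (stated 300)
- 1%: 284 / 0.99 = 286.9, so 287 (stated 290)

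Both reproduce closely. At 1%, 290 × 0.01 = 2.9, or about 3 children in total. With 1:1 allocation there are 145 per arm, so an even split is 1 to 2 children per arm.

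**3. Effect on one arm's rate**

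Let N be treated children in the arm, m those omitted, and x those non-tolerant in the FAS. The FAS rate is p = x / (N − m). If all omitted children are non-tolerant, the safety-population rate is (x + m) / N, and the shift is m(1 − p) / N.

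The documents give no value for x. Assume x = 14 and N = 145:

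| Omitted in the arm | FAS rate | Safety-population rate | Shift |
|---|---|---|---|
| 1 | 14/144 = 9.7% | 15/145 = 10.3% | 0.6 points |
| 2 | 14/143 = 9.8% | 16/145 = 11.0% | 1.2 points |
| 3 (all in one arm) | 14/142 = 9.9% | 17/145 = 11.7% | 1.9 points |

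The result depends little on x. For FAS rates from 5% to 30%, the shift is 0.5 to 0.7 points with m = 1 (0.70/145 to 0.95/145) and 1.0 to 1.3 points with m = 2 (1.40/145 to 1.90/145).

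**4. Effect on the difference between arms**

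With one child omitted on oxytocin and two on placebo, and the same x in each arm, restoring them changes oxytocin minus placebo by 0.6 − 1.2 = −0.6 points. Reversing the split gives +0.6. The sign is not determined by the plan.

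**5. The other route out of the FAS**

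A child with no baseline ABC-SW is also excluded and may have tolerated the dose. Omitting one such child raises the rate, from 14/145 = 9.66% to 14/144 = 9.72%.

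**The case against.** Several points on the other side are sound.

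- **The SAP permits exceptions.** Section 2.1.1 lets the SAP text name another population, so 3.4 does not breach that section. This stands. The mismatch is with the objective in 1.2.2 and the unqualified sentence in section 5. One could reply that section 5 does not list dose among its safety variables, but 1.2.2 places dose tolerability under safety, and no reason is given for using the FAS.
- **The protocol tries to collect the missing form.** Protocol v6.0 section 6.5 sends the week 24 questionnaires, which include the ABC, to families of early terminators. A child who stops in week 2 and returns one can still enter the FAS. This narrows the group but does not empty it: a family not reached within two weeks of the last dose needs no termination visit.
- **Early stopping is not always intolerance.** Section 3.1 lists reasons such as inconvenience and loss of contact. That is so, but the definition in 3.4 goes by dose at week 24, whatever the reason.

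A reader might infer stronger conclusions that the documents do not support:

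- *The FAS can only flatter oxytocin.* The rule applies to both arms, so the contrast may move either way, and children lacking a baseline form can move an arm's rate upward.
- *Early quitters vanish from tolerability reporting.* They remain in the disposition summaries (3.1) and in the adverse-event and withdrawal reporting (5, 5.1). Only the 3.4 summaries omit them.
- *The effect could be several points, using 5% attrition.* That rate belonged to the plan for 300 children. The 290 design rests on 1%, revised from attrition observed in the study.
- *The move away from the safety population used in SAP v1.0 is itself an error.* That text is superseded, and a difference from it proves nothing.

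**Conclusion.** The point holds as a small defect of population choice. Section 3.4 applies an efficacy set to a safety-objective measure and so omits some children who are non-tolerant by the SAP's own definition. Within an arm, omitting those children lowers the reported non-tolerance rate.

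The likely size is about 0.6 to 1.2 points in an arm. This rests on 1% attrition split evenly, 14 non-tolerant children in that arm's FAS, and every restored child being non-tolerant. The count of about 3 is close to an upper bound for this route at that attrition rate: attrition is counted from randomisation and may include children never dosed, and some early stoppers will return a form. Exclusions for a missing baseline ABC-SW come on top and could act in the other direction. The primary efficacy result is not affected.

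The missing analysis of time to early termination is a secondary consistency point that does not depend on these counts.

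**What to change.** 1. In SAP 3.4, use the safety population for the dose, exposure and target-dose tolerability summaries. The FAS may be kept for compliance.
2. Add one sentence to 3.4: for this summary, children off study drug before week 24 count as not at 48 IU per day at week 24. Restored children have no week 24 dose, so the percentage needs this rule.
3. For time to early termination, either add a descriptive summary by arm in the safety population (for example a Kaplan-Meier curve censored at week 24) or delete the phrase from 1.2.2. No formal test is needed.

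The cost is splitting one sentence, adding another, and one figure or one deletion. The dosing logs and termination records already being collected should suffice, and no dose or clinical rule is touched.

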#### Definitions:

**TOTAL Number of Sprays Prescribed** = Total number sprays prescribed per day x number of days since the last visit. NOTE: be sure to only count ½ days if subject has already taken a morning dose.

**TOTAL Number of Missed Sprays** = Total number of missed sprays according to the parent completed dosing diary. If parent does not return dosing diary, the parent can be asked how many sprays were missed.

### 3.5 Concomitant Medications

Concomitant medications will be categorized into the following groups and subgroups: **Neurobehavioral medications:** alpha adrenergic agonists, anti-anxiety medications, anti-cholinergics, anticonvulsants/mood stabilizers, antidepressants, antipsychotics, stimulants, other attention deficit hyperactivity disorder medications and sleep aids and **Other medications:** medications for gastrointestinal disorders, anti-infection medications, cough/allergy/asthma medications, heart medications, inhalation steroids, nutritional supplements, systemic steroids, and other.

Medications stopped prior to the first date of study drug dosing will be considered prior medications. We do not plan to summarize these medications. Medications taken after the first date of study drug dosing will be considered concomitant medications.

Concomitant medications for each study treatment group will be summarized according to their membership in the groups noted above. Upon request, a summary of each specific medication name will be provided.

In summaries, if a participant has taken a concomitant medication more than once, the participant will be counted only once in the total.

#### 4. EFFICACY ANALYSES

The FAS will be used as the analysis population for all efficacy analyses unless otherwise specified.

# **4.1 Efficacy Variables**

Detailed description of all efficacy variables is given in the protocol. All efficacy variables will be analyzed as change from baseline, except where noted.

#### 4.1.1 Primary Efficacy Variable

The ABC-SW score will be analyzed as the primary endpoint.

#### 4.1.2 Secondary Efficacy Variables

The following variables will be analyzed as secondary endpoints:

- Sociability Factor
- SRS-2 social motivation subscale score
- Stanford Binet-5 Abbreviated IQ (ABIQ)

#### 4.1.3 Exploratory Efficacy Variables

- Clinical Global Impression Severity (CGI-S)
- Clinical Global Impression Improvement (CGI-I)
- CGI-I will be analyzed as an endpoint mean instead of change from baseline.
- ABC subscales for irritability, stereotypy, hyperactivity, and inappropriate speech
- PDDBI-SV total score
- Caregiver strain questionnaire (CSQ) and its subscales
- Vineland 2 adaptive behavior composite score, and domain scores for daily living skills, communication and socialization. Motor skills will not be analyzed since it is only valid in young children
- Reading the Mind in the Eyes test (only in individuals with fluent speech and understanding of basic emotions)

#### 4.2 General Modelling Considerations for Efficacy Analyses

Unless otherwise specified, the primary model is mixed model with repeated measures (MMRM), with change from baseline to each post-baseline timepoint for a response variable, functioning (low versus high) as the stratification variable, center as a blocking factor, treatment (oxytocin versus placebo), week as a continuous variable, treatment and week interaction, and baseline value as a covariate, with random coefficients for the intercept and week, with an unstructured structure among the random coefficients. We will investigate the interaction of treatment, week, and functioning and adopt the most parsimonious model as the final model. Distributional assumptions will be examined using residuals. These mixed models could fail to converge or encounter difficulties based on their use of asymptotics. If they do, we will attempt to

simplify the models in order to eliminate the problems, and if necessary, move to analyses that assume compound symmetry, but use a Huynh-Feldt correction if compound symmetry fails.

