## Clarifications to Final SAP reflecting Primary Paper in the New England Journal of Medicine 05-15-2021:

- 1. Throughout the protocol and SAP, we refer to the ABC-SW, which is a modified subscale of the ABC-Lethargy, Social Withdrawal Subscale that eliminated questions 3, 32, and 53, which refer to lack of movement, in order to increase specificity for social reciprocity behaviors. In writing the primary paper, we wanted to eliminate any possible confusion with the original published ABC-Lethargy, Social Withdrawal subscale and referred to the modified scale as the ABC-modified Social Withdrawal subscale or ABC-mSW. We have changed our clinicaltrials.gov primary results to use the new nomenclature of ABC-mSW.
- 2. Reviewers pointed out that it was not entirely clear what our three secondary outcomes were. Therefore, we want to be clear that they are:
  - a. the Sociability Factor (abbreviated SF) which combines the ABC-mSW and the PDD-BI screening version in order to assess both areas of social reciprocity challenges and social skills (there was an error in the original version of the final SAP in which the sociability factor was inadvertently omitted from section 4.1.2, which has been corrected)
  - b.the Social Responsiveness Scale, 2nd Edition Social Motivation Subscale (abbreviated SRS-2-SM); c. the Stanford Binet, 5th edition Abbreviated Intelligence Quotient (abbreviated ABIQ).
- 3. Reviewers requested that we clarify what our sensitivity analyses were. They follow
  - a. Analysis using the original ABC-Lethargy, Social Withdrawal Subscale
  - b. Analysis integrating baseline (or screen if no baseline was available) plasma oxytocin level, baseline oxytocin level x treatment, and baseline oxytocin x treatment x time into the MMRM model
  - c. Analysis separately of the ABC-mSW outcome in the minimally verbal and fluently verbal subgroups.
  - d. Analysis of the ABC-mSW outcome in the per proctocol population
- 4. In the primary paper we also clarify that the full analysis set is essentially a modified intent treat sample, and that age group was dropped from the final analysis model because it was not significant.

Initial Statistical Analysis Plan for SOARS-B

Version 1.0

March 21, 2013

Study of Oxytocin in ASD to Improve Reciprocal Social Behaviors (SOARS-B)

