#### 1.3 STUDY DESIGN

This is a multicenter, randomized, double-blind, stratified, flexible dose, placebo-controlled study designed to evaluate OT in participants with ASD. OT will be given as an intranasal preparation with two different

[figure not shown]
concentrations of 8 IU per insufflation or 24 IU per insufflation. Oxytocin will be administered daily, in single doses up to 40 IU or divided doses in the morning and early afternoon as described in the protocol. Total daily dose is flexible, between 8 IU and 80 IU per day.

Participants who successfully complete screening and baseline assessments and are deemed eligible will be randomized to OT or placebo treatment in a 1:1 ratio, stratified by age group (3-6, 7-11, 12-17) and functioning (low, high), for a total of 6 strata. Randomization will not be stratified by center, as it was felt that additional stratification by center would lead to too many strata, a loss of degrees of freedom, and the potential for a grossly unequal randomization to treatments.

A schematic representation of the study design is shown in Figure 1. After screening and randomization at week 0 (W0), participants enter a double-blind treatment period of 24 weeks (W24), followed by open-label treatment with OT for 24 weeks, termination of OT at the end of week 48 (W48), and a week 53-55 (W53-55) or week 72 OFF treatment follow-up. Although the study design requires patient follow-up from week 0 to week 53-55, this SAP focuses on data analyses for the double-blind treatment period (week 0 to week 24).

Efficacy, safety, and tolerability are measured every four weeks throughout the treatment period. Participants who terminate early are asked to provide safety data through the remainder of the study. The schedule of assessments is provided in Table 1.

Figure 2: Schematic Representation of the Study Design

\*indicates safety labs and genetic sample taken. Primary outcome assessed at bolded time points.

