### 4.6 Addition of Covariates to Primary Efficacy Analysis Model

As additional secondary analyses for the primary efficacy variable, the following groups of covariates will be added separately to the model in the primary efficacy analysis and tested for their significance:

Baseline age, treatment-by-age interaction, treatment-by-age-by-week interaction.

Baseline serum oxytocin, treatment-by-oxytocin interaction, treatment-by-oxytocin-by-week interaction.

In both cases, the primary test will be the significance of treatment-by-variable-by-week interaction, and if not significant, the treatment-by-variable interaction.

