#### 4.7 Analyses of Key Secondary Efficacy Variables

The key secondary efficacy variables will be tested using the same model as in the primary efficacy analysis. For variables that were only measured at baseline and Week 24 (or the latest visit during the randomized treatment period), the change scores will be reported, and treatment group differences will be tested using two sample t-test.

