Randomization Method: We will randomize centrally, using our data management system. The UNC Data Team is familiar with this process as they have done this in our multicenter IMPACT trial. When a site needs to randomize a subject, after baseline is assessed, the coordinator opens the Randomization form. This form uses already assessed strata to randomize from the appropriate stratum. We will not stratify by site. We felt that both functional status and age group were more likely to be related to the outcome than site, and there are limits to how many strata we can have. We will stratify by functional status (high or low) and age group (3 age groups), producing 6 strata. The unblinded statistician will generate a randomization plan for each of the 6 strata, using a permuted block algorithm with randomly selected block sizes of 2 and 4, using SAS. The table will be exported to an Excel file and sent to the data manager. This can be done without having the lead statistician ever actually see the randomization plan. (He/she will debug the program and when debugged, run it with a new seed for the random number generator without seeing the results.) The database manager will import the randomization plan as a table in Access. The Randomization form

will use Visual Basic code and the values of the strata variables to enter the correct subset of the table and choose the first unused treatment. It will generate an ID number and send an email to the appropriate pharmacy, where drug will be assigned.

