# 10.1 Statistical Analysis (Please also see SAP)

General Modeling: Unless otherwise specified, we will fit a mixed longitudinal model with change from baseline to each post-baseline month (4 weeks) for a response variable, functioning (low versus high) as the stratification variable, center as a blocking factor, treatment (oxytocin versus placebo) as the between-subjects factor, week as a within-subjects factor, their interaction, and baseline as a covariate. The primary model used will be a mixed model with repeated measures (MMRM), treating week categorically and using an autoregressive (with a lag of 1) covariance structure. As a secondary sensitivity analysis, we will fit a random coefficients model treating week continuously with random coefficients for the intercept, slope, and slope squared, with an unstructured structure among the random coefficients. The primary hypothesis test of interest will be a test of treatment effect at week 24. Distributional assumptions will be examined using residuals. These mixed models could fail to converge or encounter difficulties based on their use of asymptotics. If they do, we will attempt to simplify the models in order to eliminate the problems, and if necessary, move to analyses that assume compound symmetry, but use a Huynh-Feldt correction if compound symmetry fails.

Missing Data: The mixed models used to evaluate the continuous response variables are able to handle moderate amounts of missing data provided they are missing at random. We will examine the missing at random assumption by assessing baseline differences between dropouts and completers, as well as differences in response variables up to the point of premature withdrawal. If the missing at random assumption does not appear to be tenable, we will report the mixed models results but spend additional effort characterizing treatment effect at time of premature withdrawal or the effect of not including participants with significant missing data in supplementary analyses.

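### SAP v2.0 section 4.2 leaves age group, a randomisation stratum, out of the primary model (no bias, small loss of precision of unknown size), and section 4.7 uses an unadjusted t-test

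*Combined protocol and SAP*

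**What the plan says.** **Randomisation.** SAP v2.0 section 1.3 has 1:1 allocation "stratified by age group (3-6, 7-11, 12-17) and functioning (low, high), for a total of 6 strata". The randomisation-method paragraph of protocol v6.0 section 4.5.1 agrees: "We will stratify by functional status (high or low) and age group (3 age groups), producing 6 strata".

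**Primary model.** SAP v2.0 section 4.2 uses "functioning (low versus high) as the stratification variable, center as a blocking factor", plus treatment, week, treatment by week and the baseline value, with random intercept and slope. Protocol section 10.1 names the same design factors: "functioning (low versus high) as the stratification variable, center as a blocking factor, treatment (oxytocin versus placebo) as the between-subjects factor". Neither has age group. The omission is deliberate: item 17 of the SAP change summary records that age group was removed from section 4.2.

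**Where age does appear.** Section 2.3 says that "additional models with baseline serum oxytocin, age, and functionality as covariate will be examined and tested", and section 4.6 lists "Baseline age, treatment-by-age interaction, treatment-by-age-by-week interaction". Both concern supplementary models of the primary outcome. Item 5 of the change summary adds that the predefined age group, not age in months, was used in those covariate analyses. Item 4 of the 2021 clarifications says that "age group was dropped from the final analysis model because it was not significant".

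**Endpoints with one post-baseline measurement.** For variables measured only at baseline and week 24, section 4.7 says that "treatment group differences will be tested using two sample t-test". Under the schedule of events this covers ABIQ among the three secondary endpoints (tested at screening and week 24). Through section 4.8 it also covers Vineland and Caregiver Strain among the exploratory ones.

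**The concern.** Stratifying by a prognostic factor balances it between arms, so the true sampling variance of the treatment difference no longer contains that factor's contribution. A model without the factor still counts the contribution as residual variance. The reported SE is then too large, confidence intervals too wide and the test conservative. A factor that restricts the randomisation therefore belongs in the analysis by design, whether or not it turns out to be significant.

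What is at stake is a little precision on the primary comparison, not its validity. For the section 4.7 endpoints more can be lost, because the t-test on change uses neither the baseline value nor either stratification factor, although section 4.2 uses baseline for the other endpoints.

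**Working it through.** **Inputs.** SAP v2.0 section 6: SD of change 9, difference 5, alpha 0.05, power 90%, 71 per arm per functioning stratum, final N 290 with 1% attrition. Section 2.2: two-sided tests. Protocol summary: six sites. Visits at weeks 4, 8, 12, 16, 20 and 24. The documents do not give the R² of age group, the covariance of the repeated measures or the baseline to week-24 correlation, so these are assumed below.

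**The plan's own figure.** n per arm = 2(1.960 + 1.282)² × 9²/5² = 68.1, so 69 (70 by the t distribution). The stated 71 gives about 91% power. Four cells of 71 make 284, and 284/0.99 = 287 against 290 stated. The design figure reproduces closely enough.

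**Overstatement of the SE, single-visit formula.** Ratio = 1/√(1 − R²), with R² the partial R² of age group.
- R² = 1%: 1.005
- R² = 2%: 1.010
- R² = 5%: 1.026

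**Same question in the section 4.2 random-coefficients model.** The week-24 contrast rests on each patient's fitted week-24 value. With six equally spaced visits the leverage of the last is 1/6 + 2.5²/17.5 = 0.524. If 70% of the week-24 variance lies between patients (assumed), the fitted variance is 0.7 + 0.3 × 0.524 = 0.857 of the single-visit variance. R² of 1%, 2% and 5% then becomes 1.17%, 2.33% and 5.83%, and the SE is overstated by 0.59%, 1.19% and 3.05%. Between-patient shares of 0.6 and 0.8 move the last figure only to 3.24% and 2.88%.

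**Simulation of that model** (N = 290, six strata, six centres, complete data, SD 9, no treatment effect; mean reported SE):

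| Age effect | R² | Without age group | Age group main effect | Plus age group by week |
|---|---|---|---|---|
| Constant shift | 2% | 0.9885 | 0.9783 | 0.9768 |
| Constant shift | 5% | 0.9899 | 0.9620 | 0.9605 |
| Grows with week | 2% | 0.9905 | 0.9850 | 0.9789 |
| Grows with week | 5% | 0.9881 | 0.9717 | 0.9589 |

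No model shows bias beyond simulation error, and rejection rates run from 3.8% to 5.2%. At R² = 5% a main effect recovers 0.9899/0.9620 − 1 = 2.9% if the age effect is a constant shift. If the effect grows with week, it recovers 0.9881/0.9717 − 1 = 1.7%, and the by-week term brings this to 0.9881/0.9589 − 1 = 3.0%.

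**If age group explains nothing.** In a single-visit simulation the mean SE is 1.0567 with or without it. For the random-coefficients model the cost is put at about 0.2%. In one data set whose fitted age effect is exactly zero, the 2 df cost √(278/276) − 1 = 0.36%.

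**Does non-significance bound the loss?** Suppose the reported result came from a 2-df between-patient test. With 290 × 0.99 = 287 patients and 11 parameters, df = 276 and F(0.95; 2, 276) = 3.03. Then R² < 6.06/(6.06 + 276) = 2.15%, and the SE is overstated by at most 1.1%. This bound needs a main-effect test that captures the week-24 effect. The tests named in section 4.6 are interactions, which do not limit the main effect. If the age effect grows with week, an assumed R² of 5% overstates the week-24 SE by about 3%, yet the age main effect is non-significant in about 40% to 66% of simulated trials.

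**Power and alpha.** Whole sample at 5 points: 5/(9√(2/143.5)) = 4.71, and Φ(4.71 − 1.96) = 99.7%, essentially unchanged by age group. With 71 per arm within a functioning stratum, power is 91.3% without and 91.4% with age group at R² = 1%, and 91.7% against 92.5% at R² = 5%. Actual alpha without age group is 0.049 at R² = 1% and 0.044 at R² = 5% (single-visit formula).

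**Section 4.7.** With equal SDs at both visits and correlation ρ, the variance of change is 2σ²(1 − ρ) and the ANCOVA residual variance is σ²(1 − ρ²). The SE ratio is √(2/(1 + ρ)): 1.155, 1.085 and 1.026 for ρ = 0.5, 0.7 and 0.9.

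**The case against.** The strongest reply is that no decision changes. The estimate is unbiased, any error is on the safe side, overall power at the design difference is 99.7% either way, and within-stratum power moves by less than one point. If age group has no prognostic value, adding it gains nothing. The removal was recorded in the SAP change summary, and supplementary models with age group were run. All of this stands, and it is why the point is minor. It does not make the omission preferable: the covariate is already collected, and adjusting for a stratification factor should not depend on its p-value.

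It is also fair that the section 4.7 figures measure the loss from ignoring baseline, not from ignoring age group. They are a separate point and lend no weight to the first.

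Three stronger readings are tempting and not supported:
- **The loss is capped at about 1% because age group was not significant.** The clarifications do not say which test was run, and the working shows that a non-significant main effect is compatible with about 3%.
- **Dropping age group inflated the false-positive rate.** Omitting a balanced factor makes the test conservative.
- **A prespecified term was removed from the primary model after the data were seen.** Section 4.2 of SAP v2.0 never listed age group. The clarification may refer to the covariate models of sections 2.3 and 4.6; the text does not say.

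**Conclusion.** The mismatch is real and minor. Age group restricts the randomisation but is absent from the primary model, which adjusts for functioning, centre and baseline. Adjusting for centre, although it is not a stratum, is acceptable. The treatment estimate is unbiased and the test at most slightly conservative. The documents do not allow the loss to be fixed at one figure: it is about 0.5%, 1% or 3% of the SE if age group explains 1%, 2% or 5% of the variance of week-24 change. The figures rest on those assumed shares, the assumed 70% between-patient variance and complete data. Confidence is high in the textual mismatch and moderate in the sizes.

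The unadjusted t-test in section 4.7 is a separate inefficiency. It is larger than the first unless baseline and week-24 scores are very highly correlated, and it also rests on an assumed correlation and equal SDs.

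**What to change.** 1. **SAP section 4.2:** add three-level age group (or the six strata) as a fixed effect in the primary model and in the mixed models that inherit it, kept whatever its p-value. Report the model without it as a sensitivity analysis. An age-group-by-week term is optional and helps only if the age effect grows with week.
2. **SAP section 4.7 (separate):** for ABIQ, Vineland and Caregiver Strain, replace the t-test by ANCOVA on change with baseline, functioning and age group.
3. **Clarification only:** in item 4 of the 2021 clarifications, state which model the non-significant age-group test came from, in line with item 5 of the change summary. Reconcile protocol section 4.5.1, which says both that randomisation is and is not stratified by age. It also gives blocks of 4 or 6 in one paragraph and 2 and 4 in the next.

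**Cost:** no new data or patients, 2 of about 278 degrees of freedom in the mixed models, and a few lines of text and code.
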